9.1.1.1 Collection of Specimens

Tumor biopsy samples will be obtained by core needle biopsy. A minimum of four, but ideally six, core needle biopsies will be requested: at least 3 for snap freezing for whole exome sequencing, RNA-seq, and immunoblotting, and one for formalin-fixation for immunohistochemistry (see section 9.2). It is recommended that tumor biopsies be collected using an 18 gauge needle, however this is up to the discretion of the Interventional Radiology Team of the treating institution. Standard approaches for formalin-fixation and frozen section will be used (See Appendix F and G). Specimens will be obtained pre-treatment, on-treatment (cycle 1, day 17-22 of a 28 day cycle), and at the time of disease progression.

It is not recommended to use the bone marrow biopsy instead of the tumor biopsy, however it is an option. If a bone marrow biopsy is used, please collect the following samples:

- The 10mL green top (BD Vacutainer Sodium Heparin Tube), which should be ficolled and frozen viably
- The non-heparin syringe that is transferred to a 15mL conical tube (centrifuge tube) should be snap frozen

It is not recommended to collect blood as the source of the tumor biopsy, however it is an option. A bone marrow biopsy or core biopsy are much preferred. Sites should discuss this with [name] prior to proceeding with this option. Please email the DFCI CRC or contact [name] directly if this possibility arises. If blood is used, please collect the following sample:

- whole blood in a Streck cell-free DNA tube, 4-6 mL of plasma obtained and frozen, then sent to CCPM on dry ice

9.1.1.2 Handling of Specimens

Please see the SOPs and IHC templates provided in Appendices D-G.

For formalin-fixed samples, each container should be labeled with:

- a. Protocol number (9875)
- b. Subject Study Number
- c. Pre/on/post treatment
- d. Date of collection

For fresh frozen tissue samples, biopsies should be frozen on site within 5-10 minutes of devascularization and one cryomold per specimen should be used and submitted. Each cryomold should be labeled on the bottom with the following:

- a. Protocol Number (9875)
- b. Subject Study Number
- c. Pre/on/post treatment
- d. Date of collection

The lip of each cryomold should be labeled with the core #.

9.1.1.3 Shipping of Specimens

Formalin-Fixed Samples should be sent in a securely closed container (one with a screw top/cap), this container should be placed in a secondary container (plastic zip loc bags work well) put a piece of absorbent material in the secondary container with the sample in case of leakage. This entire package along with a Specimen Submission Form (Appendix H) can then be shipped via FedEx (in their appropriate packaging), under current shipping requirements for non-infectious/hazardous human samples. Please keep SSF outside of the secondary container so it does not become wet should the primary container leak. A Specimen Submission Form should be included for each

sample submitted (see Appendix H). An FFPE block of the samples is preferable, however the tissue can be sent in just formalin if needed. Kits for shipment will *not* be provided.

Frozen tissue should be shipped on dry ice in a separate box from Formalin-Fixed tissue. A Specimen Submission Form should be included for each sample submitted.

Shipping container for Frozen Tissue should include:

- Priority Overnight Frozen Material labeling
- Dry Ice UN number
- Class 9 label

Please ship specimens via FedEx Overnight Priority to:

[name]
Dana-Farber Cancer Institute
[name]
[name]
[name]
Re: Protocol 16-712

Please note: packages must be sent for Tuesday through Friday delivery only. Do not ship on Friday or over the weekend/holidays.

For each package, complete and send DFCI Shipping Manifest(s) (Appendix H) as detailed below:

1. Complete one manifest for FFPE samples and a separate manifest for frozen tissue even if shipping on the same day.
2. Email the DFCI Shipping Manifest(s) to [contact] at the time of shipment. This office can also be reached by phone at [contact].
3. Include a printed copy of the DFCI Shipping Manifest(s) with the package.

9.1.1.4 Site(s) Performing Correlative Study

All immunostains will be performed at the Dana-Farber Cancer Institute/Brigham and Women's Hospital Hematopathology Core Laboratory (a CLIA approved laboratory) under the direction of [name] and [name]. This lab has extensive experience with these immunostains as they are standardly done on all ALCL, MCL, and DLBCL cases reviewed, respectively.

9.2 Exploratory/Ancillary Correlative Studies

9.2.1 Immunoblotting for HSP90 clients

We have extensive experience in the [name] lab with immunoblotting for several HSP90 clients in MCL and DLBCL cell lines before and following exposure to HSP90 inhibitors, and in tissue from MCL cell line and patient derived xenografts treated with either vehicle or drug (see section 2.3.2). These include BTK and pBTK, cyclin D1, CDK4, AKT and pAKT, ERK and pERK, IKK α , p100, p52, and BCL6. Our lab will immunoblot for these HSP90 clients and

others, and compare protein levels semi-quantitatively between pre- and on-treatment lymphoma cells, and at the time of disease progression. We expect to see downregulation of these proteins on treatment, and possibly upregulation of some or all of these proteins at the time of progression on drug.

9.2.1.1 Collection of Specimens

Tumor biopsy samples will be obtained by core needle biopsy. A minimum of four, but ideally six, core needle biopsies will be requested: at least 3 for snap freezing for whole exome sequencing, RNA-seq, and immunoblotting, and one for formalin-fixation for immunohistochemistry (see section 9.1). It is recommended that tumor biopsies be collected using an 18 gauge needle, however this is up to the discretion of the Interventional Radiology Team of the treating institution. Standard approaches for formalin-fixation and frozen section will be used (See Appendix F and G). Specimens will be obtained pre-treatment, on-treatment (cycle 1, day 17-22 of a 28 day cycle), and at the time of disease progression.

It is not recommended to use the bone marrow biopsy instead of the tumor biopsy, however it is an option. If a bone marrow biopsy is used, please collect the following samples:

- The 10mL green top (BD Vacutainer Sodium Heparin Tube), which should be collected and frozen viably
- The non-heparin syringe that is transferred to a 15mL conical tube (centrifuge tube) should be snap frozen

It is not recommended to collect blood as the source of the tumor biopsy, however it is an option. A bone marrow biopsy or core biopsy are much preferred. Sites should discuss this with [name] prior to proceeding with this option. Please email the DFCI CRC or contact [name] directly if this possibility arises. If blood is used, please collect the following sample:

- whole blood in a Streck cell-free DNA tube, 4-6 mL of plasma obtained and frozen, then sent to CCPM on dry ice

9.2.1.2 Handling of Specimens

Please see the SOPs and IHC templates provided in Appendices D-G.

For formalin-fixed samples, each container should be labeled with:

- a. Protocol number (9875)
- b. Subject Study Number
- c. Pre/on/post treatment
- d. Date of collection

For fresh frozen tissue samples, biopsies should be frozen on site within 5-10 minutes of devascularization and one cryomold per specimen should be used and submitted. Each cryomold should be labeled on the bottom with the following:

- a. Protocol Number (9875)
- b. Subject Study Number
- c. Pre/on/post treatment
- d. Date of collection

The lip of each cryomold should be labeled with the core #.

9.2.1.3 Shipping of Specimen(s)

Formalin-Fixed Samples should be sent in a securely closed container (one with a screw top/cap), this container should be placed in a secondary container (plastic zip loc bags work well) put a piece of absorbent material in the secondary container with the sample in case of leakage. This entire package along with a Specimen Submission Form (Appendix H) can then be shipped via FedEx (in their appropriate packaging), under current shipping requirements for non infectious/hazardous human samples. Please keep SSF outside of the secondary container so it does not become wet should the primary container leak. A Specimen Submission Form should be included for each sample submitted (see Appendix H). An FFPE block of the samples is preferable, however the tissue can be sent in just formalin if needed. Kits for shipment will *not* be provided.

Frozen tissue should be shipped on dry ice in a separate box from Formalin-Fixed tissue. A Specimen Submission Form (Appendix H) should be included for each sample submitted.

Shipping container for Frozen Tissue should include:

- Priority Overnight Frozen Material labeling
- Dry Ice UN number
- Class 9 label

Please ship specimens via FedEx Overnight Priority to:

[name]

Dana-Farber Cancer Institute

[name]

[name]

[name]

Re: Protocol 16-712

Please note: packages must be sent for Tuesday through Friday delivery only. Do not ship on Friday or over the weekend/holidays.

For each package, complete and send DFCI Shipping Manifest(s) (Appendix H) as detailed below:

1. Complete one manifest for FFPE samples and a separate manifest for frozen tissue even if shipping on the same day.
2. Email the DFCI Shipping Manifest(s) to [contact] at the time of shipment. This office can also be reached by phone at [contact].
3. Include a printed copy of the DFCI Shipping Manifest(s) with the package.

9.2.1.4 Site(s) Performing Correlative Study

All immunoblotting will be performed in the laboratory of [name] at the Dana-Farber Cancer Institute.

9.2.2 Whole exome sequencing and transcriptome analysis

Samples will also be submitted for whole exome sequencing (with paired germline samples) and RNAseq, and results will be compared between pre- and on-, and time or progression tumor samples for markers of disease response and resistance. For exome sequencing, the ABSOLUTE algorithm will be applied to determine the cancer cell fraction. Variant allele fractions for mutations present in the progression sample can then be compared to those in the pre-treatment sample after adjustment for cancer cell fractions to determine whether AT13387 (onalespib) results in a shift in the clonal architecture of lymphomas.⁸⁵ Although HSP90 classically acts at the post-translational level, some evidence indicates that it also can affect transcription.⁸⁶ We previously demonstrated in human leukemia cells that transcriptional profiling can highlight downstream pathways that are suppressed or activated in response to the degradation of HSP90 clients.⁸⁷ Transcriptional analysis by RNAseq will be performed on specimens obtained prior to beginning treatment, during treatment with AT13387 (onalespib) and then upon progression. In cases with bone marrow or peripheral blood involvement, lymphoma cells will be purified, for example by CD19 selection. Markers of response and progression will be determined by: 1) comparing gene expression patterns using GSEA⁸⁸, 2) interrogation of the Broad Institute Molecular Signatures Database⁸⁸ (MSigDB; <http://www.broadinstitute.org/gsea/msigdb/index.jsp>) and 3) Ingenuity Pathway Analysis^{89,90}, as we previously performed.⁹¹ In addition, we will interrogate the signature of progression during AT13387 (onalespib) treatment in the Connectivity Map, a database linking gene expression with drug sensitivity.⁹² Build 2.0 contains over 7,000 expression profiles representing the effects of 1,309 compounds. Compounds that correlate inversely with the signature, and therefore may abrogate it, are readily available therapeutics to block pathways that bypass HSP90 inhibition. The analysis of these exploratory biomarker studies will be retrospective, with assays performed after response evaluation for biomarker identification.

If new health information about inherited traits is found on research testing, the study doctor will let the participant know about this and the participant will then be able to choose whether or not to receive this information.

9.2.2.1 Collection of Specimens

Tumor biopsy samples will be obtained by core needle biopsy. A minimum of four, but ideally six, core needle biopsies will be requested: at least 3 for snap freezing for whole exome sequencing, RNA-seq, and immunoblotting, and one for formalin-fixation for immunohistochemistry (see section 9.1). It is recommended that tumor biopsies be collected using an 18 gauge needle, however this is up to the discretion of the Interventional Radiology Team of the treating institution. Standard approaches for formalin-fixation and frozen section will be used (See Appendix F and G). Specimens will be obtained pre-treatment, on-treatment (cycle 1, day 17-22 of a 28 day cycle), and at the time of disease progression.

It is not recommended to use the bone marrow biopsy instead of the tumor biopsy, however it is an option. If a bone marrow biopsy is used, please collect the following samples:

- The 10mL green top (BD Vacutainer Sodium Heparin Tube), which should be ficolled and frozen viably
- The non-heparin syringe that is transferred to a 15mL conical tube (centrifuge tube) should be snap frozen

It is not recommended to collect blood as the source of the tumor biopsy, however it is an option. A bone marrow biopsy or core biopsy are much preferred. Sites should discuss this with [name] prior to proceeding with this option. Please email the DFCI CRC or contact [name] directly if this possibility arises. If blood is used, please collect the following sample:

- whole blood in a Streck cell-free DNA tube, 4-6 mL of plasma obtained and frozen, then sent to CCPM on dry ice

9.2.2.2 Handling of Specimens

Please see the SOPs provided in Appendices F and G

For formalin-fixed samples, each container should be labeled with:

- a. Protocol number (9875)
- b. Subject Study Number
- c. Pre/on/post treatment
- d. Date of collection

For fresh frozen tissue samples, biopsies should be frozen on site within 5-10 minutes of devascularization and one cryomold per specimen should be used and submitted. Each cryomold should be labeled on the bottom with the following:

- a. Protocol Number (9875)
- b. Subject Study Number
- c. Pre/on/post treatment
- d. Date of collection

The lip of each cryomold should be labeled with the core #.

9.2.2.3 Shipping of Specimens

Formalin-Fixed Samples should be sent in a securely closed container (one with a screw top/cap), this container should be placed in a secondary container (plastic zip loc bags work well) put a piece of absorbent material in the secondary container with the sample in case of leakage. This entire package along with a Specimen Submission Form (Appendix H) can then be shipped via FedEx (in their appropriate packaging), under current shipping requirements for non-infectious/hazardous human samples. Please keep SSF outside of the secondary container so it does not become wet

should the primary container leak. A Specimen Submission Form should be included for each sample submitted (see Appendix H). An FFPE block of the samples is preferable, however the tissue can be sent in just formalin if needed. Kits for shipment will *not* be provided.

Frozen tissue should be shipped on dry ice in a separate box from Formalin-Fixed tissue. A Specimen Submission Form (Appendix H) should be included for each sample submitted.

Shipping container for Frozen Tissue should include:

- Priority Overnight Frozen Material labeling
- Dry Ice UN number
- Class 9 label

Please ship specimens via FedEx Overnight Priority to:

[name]

Dana-Farber Cancer Institute

[name]

[name]

[name]

Re: Protocol 16-712

Please note: packages must be sent for Tuesday through Friday delivery only. Do not ship on Friday or over the weekend/holidays.

For each package, complete and send DFCI Shipping Manifest(s) (Appendix H) as detailed below:

1. Complete one manifest for FFPE samples and a separate manifest for frozen tissue even if shipping on the same day.
2. Email the DFCI Shipping Manifest(s) to [contact] at the time of shipment. This office can also be reached by phone at [contact].
3. Include a printed copy of the DFCI Shipping Manifest(s) with the package.

9.2.2.4 Sites Performing Correlative Study

Whole exome sequencing and RNASeq will be done at the Broad Institute.

10. STUDY CALENDAR

Baseline evaluations are to be conducted within 2 weeks prior to start of protocol therapy. Scans and x-rays, including LVEF evaluation, must be done ≤ 6 weeks prior to the start of therapy and bone marrow biopsy must be done ≤ 6 weeks prior to the start of therapy. In the event that the patient's condition is deteriorating, laboratory evaluations should be repeated within 48 hours prior to initiation of the next cycle of therapy.

		Cycle 1								Cycle 2+		
	Pre-Study ^a	D 1	D 2	D 8	D 9	D 15	D 16	D 17	D 18	D 1,8,15	D 2,9,16	Off Treatment ⁱ
AT13387 (onalespib)		A	A	A	A	A	A			A	A	
Informed consent	X											
Demographics	X											
Medical history	X											
Detailed eye exam ^b	X											
Concurrent meds	X	X-----X										
Physical exam	X	X		X		X				X		X
Vital signs	X	X	X	X	X	X	X			X	X	X
Height	X											
Weight	X	X	X	X	X	X	X			X	X	X
Performance status	X	X		X		X				X		X
CBC w/diff, plts	X	X		X		X		X		X		X
Serum chemistry ^c	X	X		X		X		X		X		X
EKG ^d	X	X		X		X				X ^d		X
LVEF evaluation (TTE or MUGA)	X											
Adverse event evaluation ^e		X-----X										X
Bone marrow biopsy	X											X ^f
Blood sample for germline sequencing ^g	X											
Radiologic evaluation												
FDG-PET/CT scans	X									FDG-PET/CT should be performed every 8 weeks +/- 3 days		X
CT chest/abdomen/pelvis	X									CT scans should be performed every 8 weeks +/- 3 days		X ⁱ
B-HCG ^h	X											
Tumor biopsy ^k	X							X				X

A: AT13387 (onalespib): 160mg/m²/dose as assigned
a: All screening must take place within 2 weeks of the start of therapy, except for scans, which must occur within 6 weeks, and the screening bone marrow biopsy, which must occur within 6 weeks, prior to the start of therapy.
b: All patients will have a detailed eye exam by an ophthalmologist during screening to be used as a baseline eye exam for comparison, should ocular toxicity later develop. There are no protocol-specific tests required for this eye exam. If patients develop eye symptoms during treatment, an additional eye examination may be conducted at the investigator's discretion. See appendix I for an example of an eye exam work-up. Using this eye exam form is *not* required.
c: Albumin, alkaline phosphatase, total bilirubin, bicarbonate, BUN, calcium, chloride, creatinine, glucose, LDH, phosphorus, potassium, magnesium, total protein, SGOT [AST], SGPT [ALT], sodium, uric acid.
d: Cycle 2 and on, electrocardiograms (EKGs) will be done on day 1 of each cycle. EKGs should be done per standard of care at the treating institution. EKGs are not required to be in triplicate, but if there is an issue with a QTc value on the single EKG, an average QTc is acceptable on three triplicate EKGs if it makes a patient eligible for treatment.
e: Adverse event and concomitant medication evaluation will be assessed at each visit by the clinical trial personnel.
f: If bone marrow biopsy is negative at screening, it does not need to be repeated. If the bone marrow biopsy is involved at baseline, it must be repeated in order to confirm a complete response (CR).
g: To be collected in 1 x 4 mL purple top EDTA tube. However, a minimum of 1 mL of blood is needed so any tube size that meets this 1 mL minimum is acceptable. This can be shipped along with the frozen tissue.
h: Serum pregnancy test (women of childbearing potential).
i: Off-treatment evaluation. Patients who come off treatment for progression will have telephone follow-up every 6 months for up to 1 year

- | |
|--|
| 
for OS endpoints. Patients who come off treatment for reasons other than progression will have CT scans (see below) at 6 and 12 months, or until the time of progression or next therapy, for PFS and DOR endpoints.
 
j: CT scans will be repeated at 6 and 12 months, or until the time of progression, for patients who come off study for reasons other than disease progression.
 
k: Biopsy or sample of most accessible tissue, which may be bone marrow, body fluid, lymph node, or other tumor site. The sample should be from the same tumor source (ie body fluid, bone marrow, lymph node, or other tumor site) at each timepoint. This is distinct from the bone marrow biopsy required at screening for lymphoma staging. However, if the bone marrow is involved at screening, this can be used as the site of tumor biopsy for patients during pre-treatment, cycle 1 and at the time of progression. Biopsies during cycle 1 should optimally be done on day 17, but can be done between days 17-22.
 |
|--|

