3.1.3.2 MCL

Patients must have disease that has relapsed and or is refractory to prior therapy, which must have included a multiagent chemotherapy regimen and prior ibrutinib or other BTK inhibitor therapy. Patients must have relapsed following or be ineligible for, or refuse, autologous stem cell transplant.

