3.2 Exclusion Criteria

- 3.2.1 Patients who have had chemotherapy or radiotherapy within 4 weeks (6 weeks for nitrosoureas or mitomycin C) prior to entering the study or those who have not recovered from adverse events due to agents administered more than 4 weeks earlier. Steroids for symptom palliation are allowed but must be either discontinued or on stable doses at the time of initiation of protocol therapy.
- 3.2.2 Patients who are receiving any other investigational agents. All investigational agents other than ibrutinib must have been discontinued at least 4 weeks prior to beginning treatment. Prior ibrutinib therapy must have been discontinued at least 2 weeks prior to beginning therapy.
- 3.2.3 Patients with known leptomeningeal or brain metastases should be excluded from this clinical trial because of their poor prognosis and because they often develop progressive neurologic dysfunction that would confound the evaluation of neurologic and other adverse events. Imaging or spinal fluid analysis to exclude CNS involvement is not required, unless there is clinical suspicion by the treating investigator.
- 3.2.4 History of allergic reactions attributed to compounds of similar chemical or biologic composition to AT13387 (onalespib).

- 3.2.5 Uncontrolled intercurrent illness including, but not limited to, ongoing or active infection, symptomatic congestive heart failure, unstable angina pectoris, cardiac arrhythmia, or psychiatric illness/social situations that would limit compliance with study requirements.

There will be no exclusion of patients with known visual impairment or symptoms, including by not limited to peripheral flashes (photopsia), blurred or double vision, floaters, color distortion and dimness, difficulties with light/dark accommodation, tunnel vision or other field defects, halos, apparent movement of stationary objects, and complex disturbances. Patients will have a baseline ophthalmologic exam to serve as a point of comparison and further exams as needed should visual symptoms develop. No pre-treatment eye exam findings or ocular symptoms have been associated with an increased risk of ocular toxicity seen with AT13387.

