11. MEASUREMENT OF EFFECT

11.1 Antitumor Effect

All patients will have a baseline PET/CT scan within 6 weeks prior to the start of therapy. For the purposes of this study, patients should be re-evaluated for response by PET/CT scans every 8 weeks. In addition, a bone marrow aspirate and biopsy are required within 6 weeks before the 1st treatment for all patients. If the initial marrow shows involvement, repeat marrow is required to confirm a CR. If the initial marrow is negative, further bone marrow biopsy is not required. The marrow should be sent for aspirate, core pathology, flow cytometry, and cytogenetics.

Response and progression will be evaluated in this study using the International Harmonization Project for lymphoma criteria.¹⁰⁴

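### Does the baseline scan have to be timed from the last dose of prior therapy as well as from the first onalespib dose?

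*Combined protocol and SAP*

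**What the plan says.** The scan window has one anchor, the start of onalespib. The introduction to Section 10 says "Scans and x-rays, including LVEF evaluation, must be done ≤ 6 weeks prior to the start of therapy", footnote a says "All screening must take place within 2 weeks of the start of therapy, except for scans, which must occur within 6 weeks", and Section 11.1 repeats it: "All patients will have a baseline PET/CT scan within 6 weeks prior to the start of therapy". None of these mentions the last dose of earlier treatment.

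The washouts in Section 3.2 are set independently and are mostly shorter than six weeks:

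- Ibrutinib (3.2.2): "Prior ibrutinib therapy must have been discontinued at least 2 weeks prior to beginning therapy".
- Other investigational agents (3.2.2): "All investigational agents other than ibrutinib must have been discontinued at least 4 weeks prior to beginning treatment".
- Chemotherapy and radiotherapy (3.2.1) exclude "Patients who have had chemotherapy or radiotherapy within 4 weeks (6 weeks for nitrosoureas or mitomycin C) prior to entering the study".
- Palliative steroids (3.2.1): "Steroids for symptom palliation are allowed but must be either discontinued or on stable doses at the time of initiation of protocol therapy".

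Prior BTK inhibition is compulsory only in mantle cell lymphoma, where Section 3.1.3.2 describes prior therapy "which must have included a multiagent chemotherapy regimen and prior ibrutinib or other BTK inhibitor therapy". Section 3.1.2 requires progression after any earlier radiation. Sections 3.1.3.1 to 3.1.3.3 require relapsed or refractory disease but do not date the relapse relative to the scan.

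**The concern.** Response is measured against the baseline scan. If a patient is scanned and then takes further doses of the previous drug, any later shrinkage from that drug falls between baseline and the first on-study assessment and is credited to onalespib. The protocol guards against this for radiation by requiring later progression. It has no equally explicit rule for systemic therapy. Tumor growth between an old scan and day 1 would have the opposite effect and could hide a response.

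The response rate is primary, there is no control arm, and Section 13.1 decides each two-stage cohort on at least 1 response in 10 and then at least 3 in 20. One wrongly classified patient could matter.

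**Working it through.** **1. The plan's own figures.** The Section 13.1 rule is to stop at 0/10 and otherwise succeed at 3 or more of 20. P(success) = Σ over x ≥ 1 of Bin(x; 10, p) × P(X₂ ≥ 3 − x), with X₂ ~ Bin(10, p). This gives 0.0686 at p = 5% and 0.8820 at p = 25%. Early stopping is 0.95¹⁰ = 0.599 and 0.75¹⁰ = 0.056. The stated 6.9%, 88%, 60% and 5.6% all reproduce, so the design arithmetic is sound and the question is only about measurement timing.

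**2. How far the scan can precede the last prior dose.** Maximum scan age is 6 × 7 = 42 days. Subtract the shortest permitted gap from last dose to day 1:

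| Prior therapy | Shortest gap (days) | Scan ahead of last dose by up to |
|---|---|---|
| Ibrutinib | 14 | 42 − 14 = 28 |
| Other investigational agent | 28 | 42 − 28 = 14 |
| Chemotherapy | 28 to 35 | 42 − 28 = 14 to 42 − 35 = 7 |
| Nitrosoureas, mitomycin C | 42 | 0 |

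The chemotherapy washout runs to study entry. Taking entry as registration (an assumption), Section 4.4 allows up to 7 more days before dosing, hence the range.

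**3. How long carry-over would have to last.** Section 10 schedules response imaging every 8 weeks ± 3 days, so the first falls no earlier than 56 − 3 = 53 days after day 1. That is at least 14 + 53 = 67 days after ibrutinib, and 28 + 53 = 81 days after chemotherapy or another investigational agent.

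**4. Effect on the size threshold.** Let g be the proportional size change between scan and day 1. The on-drug decrease that shows as 50% is 1 − 0.5/(1 + g). The documents give no value for g; these are assumed:

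| g | On-drug decrease needed |
|---|---|
| −20% | 37.5% |
| −10% | 44.4% |
| 0 | 50% |
| +10% | 54.5% |
| +20% | 58.3% |

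Even after an unseen 20% shrinkage, onalespib must still produce more than a one-third reduction. These figures cover size-based partial response only. Section 11.1.2.1 also allows a complete response when a residual mass is PET negative.

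**5. What one misclassified patient would do.** With one stage 1 non-responder read as a response and the other 19 at 5%, success needs at least 2 of 19: 1 − 0.95¹⁹ − 19 × 0.05 × 0.95¹⁸ = 0.245, against 0.059 if that patient is read correctly. In the other direction, with the other 19 at 25%, missing one genuine stage 1 responder lowers P(success) from 0.969 to 0.853. These values apply to any misread patient from any cause. They do not show how often scan order produces one.

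**6. Separating the two directions.** Crediting prior therapy's shrinkage requires the scan to come before the last prior dose. Masking by growth does not: it needs only an interval between scan and day 1, which can reach six weeks even when the scan follows every prior dose. Linking the scan to the last dose would therefore leave masking untouched.

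**7. What a change could still achieve.** Section 13.1 closes enrollment as of October 2019, and the mantle cell cohort in February 2019. A scan-order rule written now has no patient to apply to. A sensitivity response rate that disallows responses with a pre-last-dose baseline can only lower the count, would discard genuine responses too, and recovers none hidden by growth.

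**The case for a change.** The best argument for acting is that a decision resting on three patients should not depend on an unrecorded sequence of dates, and that recording it is cheap. The protocol accepts the principle for radiation. Central review under Section 11.1.5 reads the same baseline and cannot correct its timing. Nor is 28 days a ceiling for every drug: Section 3.2 names no washout for a marketed BTK inhibitor other than ibrutinib or for a marketed ALK inhibitor, although Sections 3.1.3.1 and 3.1.3.2 contemplate both. Steroids may also be stopped between scan and day 1.

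The timing gap is real, and so is the point about unnamed agents. But the relapsed or refractory requirement is a partial counterpart to the radiation rule. A false partial response would need a tumor that had escaped its last treatment to shrink by half because of that treatment, with no new sites and no growth in other masses, and still show it about ten weeks or more after the last named agent. The calculation in step 5 assumes the misread patient rather than making one likely. A sensitivity analysis is also a crude split: a scan one day after the last dose passes, although late shrinkage is still possible. An exemption for scans that documented progression on the last agent would readmit many of the scans in question.

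**Conclusion.** No change to the plan. A compliant baseline scan can precede the last ibrutinib dose by up to 28 days and other named agents by 0 to 14 days. The exposure is mainly in the mantle cell cohort, and no rate of carry-over can be taken from the documents. The judgment that it is rare rests on the eligibility requirement for relapsed or refractory disease, the 50% threshold, and the interval of at least 67 days from ibrutinib to the first response scan. If residual shrinkage were common despite these, the concern would carry more weight. Growth before day 1 is a conservative error arising from a practical imaging window.

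The decisive point is that amendment gains nothing. Baselines are fixed, the primary response rate and decision rules would stay as they are, and Section 13.5.2 already keeps sub-analyses from supporting efficacy conclusions. An analyst who wants to reassure readers can list, for each responder, the intervals from last prior systemic dose to scan and from scan to day 1, and flag any response whose baseline preceded the last dose without documenting progression on that agent. Scan dates accompany the images sent for central review, and last-dose dates are needed to verify the washouts, so this needs no amendment.
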